Lack of research: The OECD report “Understanding effective approaches to promoting mental health and preventing mental illness” from 2017 concluded that there is a sound and quite extensive evidence base for effective and cost effective actions to promote mental wellbeing and prevent mental ill-health[21]. There are, however, few studies on ways to enhance wellbeing in the general population, and especially through web-based universal interventions. A few meta-analyses have been published, showing that face-to-face delivered positive psychological interventions are effective in improving wellbeing, with effect sizes of Cohen’s d in the range of 0.2-0.3. Sin and Lyubomirsky[22] concluded in their meta-analysis that positive psychology interventions significantly enhance wellbeing (mean $r=0.29$) and decrease depressive symptoms (mean $r=0.31$). A later meta-analysis by Bolier et al. in 2013[23] showed that the standardized mean difference was 0.34 for SWB (life satisfaction and positive affect), 0.20 for psychological wellbeing (PWB [optimal functioning in terms of e.g. mastery, hope, purpose in life]) and 0.23 for depression. Both meta-analyses indicate small, but significant effects for positive psychology interventions. A more recent review and meta-analysis, testing multi-component positive psychological interventions in both clinical and non-clinical samples, reported standardized mean effects of 0.34 for SWB, 0.39 for PWB, 0.29 for depression and 0.35 for anxiety and stress, indicating small to moderate effects[24]. Another recent meta-analysis looked at the effects of a wide range of RCT studies on positive psychology intervention targeting non-clinical population. This meta-analysis included both interventions using technology-assisted methods and traditional methods

(face-to-face). Results showed that positive psychology interventions increase wellbeing. The overall effect size was 0.23; 0.08 for PWB, 0.22 for SWB, and 0.43 when the studies targeted both types of well-being. Interventions based on traditional methods were more effective than those that used technology-assisted methods. However, technology-assisted interventions were effective too (0.27). This meta-analysis concludes that it is a lack of empirical studies with a aim to understand the success of wellbeing interventions via technology[25].

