1.3 Research questions and hypotheses, theoretical approach and methodology

Main hypothesis: The web-based intervention 5WaysA will improve wellbeing and mastery and hence provide the municipalities with an effective measure for mental health promotion.

Research questions:

1. *To what extent does participation in the web-based 5WaysA intervention lead to improved wellbeing, mental health and mastery in the general population?*
2. *To what extent are the effects short-term and long-term (i.e., 10 weeks and 12 months)?*
3. *What mechanisms explain potential improvements in wellbeing?*
 - a) *For whom is this intervention effective (i.e., is the effect moderated by e.g. gender, age, education)?*
 - b) *What mechanisms (e.g., regular practicing of 5Ways actions, increased social activity or support) explain intervention effects?*

Sample: The sample consists of participants from the general population in Norwegian municipalities. A cooperation with public health alliances in the Viken and Trøndelag regions, as well as Sunne kommuner, the Norwegian WHO Healthy Cities network, has already been established. Public health coordinators in all of the municipalities will be involved in recruitment. Invitations to participate will be distributed via emails, the municipalities' web sites, social media, local newspapers, citizen panels (e.g., *Innbyggerpanelet* in Bærum) and related means. We plan to recruit a minimum of 1500 participants. The participants will be randomized to either an intervention group ($n=750$) or one of two wait-list control groups (active control group, $n=375$) (passive control group, $n=375$), receiving the intervention five months later. Citizen panels, like the one we will recruit from in Bærum, invites inhabitants to contribute with experiences and opinions about their lives in the municipality and about municipal services. The citizens' opinions contribute to new understandings, new ideas, innovative solutions and development. All participating regions and networks involved in our study have a strong tradition for involving the citizens in their work and have implemented wellbeing in their regional strategies.

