Design: The design is a randomized controlled trial (RCT), with one intervention group and two wait-list control groups. The goal with this design is to demonstrate the initial efficacy and feasibility of the 10 week 5WaysA intervention. We choose an RCT with two wait-list control groups, where one wait-list is writing activity log and the other is passive while waiting. We add the active control because we are aware of the limitations in passive wait-list control group conditions. However, both wait-list control groups will know they are waiting for an intervention, which can in turn produce demand characteristics. The intervention group will receive the 5WaysA intervention within a few weeks after announcing their interest in participating in the study. The wait-list control groups will receive the 5WaysA intervention 5 months after the intervention group had the intervention. The active wait-list control group is encouraged to write an activity log every week. The passive wait-list control group is not getting any tasks while they are waiting, other than a questionnaire. Figure 2 shows the time line for recruiting, randomizing and the schedule for intervention and measurement points (M).

Power analysis: We assume that we can recruit a minimum of 1500 participants, but high drop-out is expected. An a priori power analysis was conducted using G*Power3[40] to test the interaction effect in a mixed ANOVA, using a two-tailed test, assuming a small effect size ($f = .10$), and an alpha of .05. The assumed effect size ($f=0.1$) was chosen as it is of the same magnitude (lower bound) as has been reported by other universal interventions with wellbeing as the outcome measure[41]. The result showed that if we attained a total sample of 750 participants at our second measurement point (attrition of 50 %), we would have power of .999 to detect a group by time interaction. The high level of statistical power will enable us to investigate both moderators and mediators.

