Procedures: The webinar will be a live lecture with an independent trained facilitator. Questionnaires will be administrated and distributed by the project manager using the Nettskjema and Services for sensitive data (TSD) tools. The measurements for the intervention group will be conducted when the participants register to participate (baseline, just before the main webinar) (M1), at the booster session webinar one months after the completed main webinar (M2), 10 weeks after the main webinar (M3), five months after the main webinar (when control groups are starting) (M4) and 12 months after the intervention is completed (M5). Control groups will be measured when the participants register to participate (baseline, just before the main webinar) (M1), when the interventions group has completed the intervention (M2), when they start the intervention (main webinar) (M3), at the booster session one months after the completed main webinar (M4), ten weeks after the main webinar (M5) and 12 months after the intervention is completed (M6)

Data analysis: The effect analysis will involve a comparison of self-reported wellbeing at different measurement points, using a two-way mixed measures ANOVA. In addition, we will run a longitudinal analysis using linear mixed (multilevel) models on the data from all five measurement time points. Mixed modelling is a flexible way to handle unbalanced data in case of non-registration and repeated observations. The models allow us to investigate the effects of the intervention and test the hypotheses of group and individual development in wellbeing while controlling for both stable and time-varying covariates.

Ethics and privacy: All the participants will receive a letter of information about the study, also specifying the requirements of The Regional Committees for Health Research Ethics (REK). A written consent from all participants in all groups will be obtained. All sensitive personal information will be handled according to GDPR requirements. Data will be stored and analyzed under the Services for sensitive data (TSD) at UiO. The study will be preregistered in Open Science Network/Clinicaltrials.gov.

Risks: There is a low probability that this study leads to any disadvantage, damage or risk for the participants. The activities they are encouraged to engage in are universal, general and easy to adapt to differences in age, culture, socioeconomic background and state of health.

| Risk | Consequences | Planned measures |

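### The powered effect analysis is a mixed ANOVA that in standard form uses completers only, with 50% attrition assumed; the mixed model suited to missing data is also planned, but nothing says which of the two decides

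*Combined protocol and SAP*

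**What the plan says.** All of this is in section 1.3 of the combined protocol and SAP.

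- **Data analysis, first sentence:** "The effect analysis will involve a comparison of self-reported wellbeing at different measurement points, using a two-way mixed measures ANOVA".
- **Power analysis:** the test powered is the group-by-time interaction in a mixed ANOVA. High dropout is expected, and the stated power of .999 applies "if we attained a total sample of 750 participants at our second measurement point (attrition of 50" %).
- **Data analysis, second sentence:** "In addition, we will run a longitudinal analysis using linear mixed (multilevel) models on the data from all five measurement time points". The reason given is that "Mixed modelling is a flexible way to handle unbalanced data in case of non-registration and repeated observations". The paragraph then also gives these models the job of examining intervention effects and testing hypotheses about how wellbeing develops, with covariates.
- **Procedures:** the label M2 falls at different times. In the intervention arm it is "at the booster session webinar one months after the completed main webinar (M2"); in the controls it is "when the interventions group has completed the intervention (M2").
- **Sample:** 750 are randomised to intervention and 375 to each of two wait-list arms.

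The supplied text does not name a primary analysis, define an analysis population, give a missing-data rule for the ANOVA, or say what happens if the two analyses disagree.

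**The concern.** A two-way mixed ANOVA in standard form needs every included measurement from every participant. That is general knowledge about the method rather than a statement in the plan, but powering on the 750 expected to remain fits it. With two time points, the interaction test is a comparison of mean change among completers, so half of those randomised may not contribute.

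The comparison of change keeps the benefit of randomisation only if those retained are similar across arms in whatever drives their change. The arms are asked to do different things: a webinar, booster and twice-weekly SMS in one, and a weekly log or only a questionnaire in the others. Retention could therefore relate to wellbeing differently by arm. If it does, high power offers no protection, because a large sample estimates the wrong quantity precisely. With two unranked effect analyses, the lead result could also be chosen after both have been seen.

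**Working it through.** **1. The plan's own power figure.** Inputs from the Power analysis paragraph: f = .10, alpha = .05, N = 750. Two time points and a correlation of .5 between them are assumed, as the plan states neither. The G*Power interaction formula gives noncentrality f² × N × m / (1 − r) = 0.01 × 750 × 2 / 0.5 = 30. Power is .9998 with two groups (df 1, 748) and .9992 with three (df 2, 747). The stated .999 reproduces.

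**2. Bias of the completer ANOVA under baseline-related retention.** Assumptions, none of them in the documents: 50% retained in each arm, the two control arms pooled, scores in SD units, and logistic retention with odds ratio (OR) 1.5 per SD of baseline in the intervention arm only.

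By numerical integration, the mean baseline of those retained is 0.195 SD in the intervention arm and 0 in the controls. Because of regression to the mean, change among completers is off by

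bias = −(1 − r) × (m_int − m_ctl) = −(1 − r) × 0.195.

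The standard error is √(2(1 − r)) × √(1/375 + 1/375). With z = |bias|/SE, the null rejection rate is Φ(z − 1.96) + Φ(−z − 1.96).

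| r | Absolute bias (SD) | SE | z | Rejection under no effect |
|---|---|---|---|---|
| .5 | 0.0975 | 0.073 | 1.34 | .267 |
| .7 | 0.0585 | 0.057 | 1.03 | .179 |
| .8 | 0.0390 | 0.046 | 0.84 | .135 |

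For scale, section 1.1 reports that "technology-assisted interventions were effective too (0.27"); the three biases are 36%, 22% and 14% of that figure. The bias does not depend on the true effect.

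**3. Direction and strength.** OR 1.5 understates benefit. OR 0.67 in the intervention arm gives a retained mean of −0.193 and overstates benefit by nearly the same amounts. OR 1.2 (retained mean 0.090) gives 0.045, 0.027 and 0.018 SD; OR 2 (0.313) gives 0.157, 0.094 and 0.063 SD. With OR 1.5 in both arms the retained means cancel and the bias is zero.

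**4. The mixed model in the same setting.** A maximum-likelihood model with a common baseline mean, simulated with 1 million per arm and an assumed true effect of 0.20, returns 0.201 / 0.201 / 0.199 at r = .5 / .7 / .8. The completer change comparison returns 0.105 / 0.142 / 0.160.

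**5. Where the mixed model is not clean.** Suppose retention depends on improvement in the first month (OR 1.5 per SD of that change), with equal correlations and a true effect of 0.20.

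- *Intervention arm only.* The completer bias is 0.5 × 0.195 × √(2(1 − r)) = 0.098 / 0.076 / 0.062, so the ANOVA gives about 0.30 / 0.28 / 0.26. If dropouts gave a one-month score, the mixed model recovers 0.20. If they did not, it corrects only for baseline and keeps a bias of r × 0.195 × √((1 − r)/2) = 0.049 / 0.053 / 0.049, giving about 0.25.
- *Both arms equally.* The ANOVA gives about 0.20 (0.196 in a trial-size simulation at r = .7). If intervention dropouts gave one-month scores, which controls do not have, the residual of about 0.05 stays in the control arm only. The mixed model then gives about 0.15.

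**The case against.** **The mixed model is already planned as an effect analysis.** This stands. A reader who stops at the opening words of the second sentence might infer that the model is merely supportive, but the same paragraph assigns it effect estimation and hypothesis testing. The fair reading is two effect analyses, with the powered one apparently leading and no stated ranking. The gap is one of priority; a suitable method is present.

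**The harm is assumed.** This also stands. The documents give no dropout mechanism, no retention difference by arm and no baseline–follow-up correlation. A reader might infer that the trial's result will be biased, or biased in favour of the intervention; the documents support neither. There is no bias if dropout is unrelated to outcome or depends on baseline equally in both arms, and little if early improvement drives it equally in both.

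**The ANOVA might use the one-month scores.** A reader might infer that it cannot, since controls have no measurement then. The plan does not settle this: both arms have an M2, and an ANOVA paired by label would use those scores at mismatched times.

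**The mixed model is not always better.** Correct, as step 5 shows. This argues for stating its assumption and adding sensitivity analyses; it does not argue for leaving the choice open.

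**Preregistration is promised and could name the primary analysis.** It could, but the plan does not say that it will.

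**Conclusion.** The concern holds as a gap in priority and missing-data handling. The plan leads with, and powers, a test that by standard practice is limited to completers while assuming that half the sample is lost. It does not rank that test against the mixed model.

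The size is conditional. For a moderate baseline dependence in one arm (OR 1.5 per SD, 50% retained per arm, controls pooled), the bias is about 0.10 to 0.04 SD and the false-positive rate 27% to 13% as the correlation goes from .5 to .8. This is neither a bound nor a forecast, since weaker dependence gives less and stronger gives more. The power figure is not at fault. The matter should be fixed before analysis. Confidence is medium, because the completer-only form is inferred and the dropout mechanism is unknown.

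**What to change.** In section 1.3, Data analysis, name the likelihood-based linear mixed model as the deciding analysis and specify:

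- all randomised participants with any measurement are included;
- baseline wellbeing is a covariate or is constrained equal across arms;
- time is entered as actual weeks since baseline, because M2 falls at different times in the arms;
- the arm contrast at 10 weeks is the estimate, with a statement of whether the two control arms are pooled;
- missing at random is the stated assumption.

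Keep the mixed ANOVA as a sensitivity analysis. Add a second one that shifts non-responders' outcomes by arm over a stated range.

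The cost is wording and slightly more complex reporting; no new data are needed. The change removes bias from baseline-related dropout but not from every mechanism. Against an assumed true 0.20, the mixed model can still give about 0.25 (one-arm dropout after early improvement, no one-month score from dropouts) or about 0.15 (equal early-improvement dropout, with one-month scores from intervention dropouts). The two sensitivity analyses are there to expose those cases.

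### The planned effect test compares raw change from baseline; adjusting for the M1 score already collected would be more precise, by an amount that depends on a correlation the plan does not state

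*Combined protocol and SAP*

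**What the plan says.** All of this is in section 1.3 of the combined protocol and SAP.

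- **Data analysis.** "The effect analysis will involve a comparison of self-reported wellbeing at different measurement points, using a two-way mixed measures ANOVA". No covariate is attached to this analysis.
- **Data analysis, second model.** "In addition, we will run a longitudinal analysis using linear mixed (multilevel) models on the data from all five measurement time points". The text says that this model can control for fixed and time-dependent covariates. It does not name them, and it does not say whether M1 enters as a covariate, as an outcome with its own mean in each arm, or as an outcome with one mean common to all arms.
- **Power analysis.** G*Power, "using a two-tailed test, assuming a small effect size ($f = .10$), and an alpha of .05". With 750 of 1500 participants left at the second measurement point, the conclusion is that "we would have power of .999 to detect a group by time interaction". No correlation between repeated measures is given.
- **Sample.** Three arms: 750 intervention, 375 active wait-list, 375 passive wait-list.
- **Procedures.** M1 is taken in the intervention arm and in both control arms. After M1, the times shared before the controls are treated are 10 weeks (intervention M3, control M2) and 5 months (intervention M4, control M3). The one-month booster visit before crossover exists in the intervention arm only.

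**The concern.** With a baseline and one follow-up, the interaction F test in a two-way mixed ANOVA is algebraically the between-arm test on follow-up minus baseline. That subtracts the whole of M1, with a weight of 1, where the efficient weight is the regression slope of follow-up on M1 (equal to r when the SDs are equal). It also treats the baseline difference between arms as something to estimate, although randomisation makes it zero in expectation.

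What is at stake is precision, not validity. The plan expects to lose half its sample, lists too small a sample among its risks, and relies on its power to look at moderators and mediators. In that setting, unused information in a variable already collected has value, most of all for contrasts smaller than the main one, such as intervention against the active control alone.

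**Working it through.** **Inputs from the plan:** f = .10, two-sided alpha .05, N = 750 analysed, three arms allocated 2:1:1. Halving each arm gives 375 / 187.5 / 187.5.

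**Assumptions:** r from .3 to .9, since the plan states none; equal SDs at both times; attrition equal across arms; 0.20 SD as a smaller effect, the lower end of the 0.2 to 0.3 that section 1.1 cites for face-to-face interventions.

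**1. The plan's figure.** In the G*Power form for a within-between interaction, lambda = N·f²·m/(1-r). With m = 2 time points and r = .5, lambda = 750 × .01 × 2 / .5 = 30 on 2 and 747 df, and power is .9992. The stated .999 reproduces for three groups, two time points and r = .5. At r = .3 it would be .990. Other combinations also come close, so this does not prove which r was used.

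**2. Variances per participant, in units of SD².**
- Change score: 2(1-r)
- M1-adjusted: 1-r²
- Ratio: (1-r²) / [2(1-r)] = (1+r)/2, so the cut is (1-r)/2

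| r | change | adjusted | ratio | cut |
|---|---|---|---|---|
| .3 | 1.40 | .91 | .65 | 35% |
| .5 | 1.00 | .75 | .75 | 25% |
| .7 | .60 | .51 | .85 | 15% |
| .9 | .20 | .19 | .95 | 5% |

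A simulation of 6000 trials with 375 per group gave ratios of .74 at r = .5 and .85 at r = .7. Both estimators were centred on the true 0.20. Expressed as sample size, 750 adjusted participants match 750/.75 = 1000 on change scores at r = .5, or 750/.85 = 882 at r = .7.

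**3. Power at the plan's own inputs.** In a balanced two-by-two layout, f = .10 in this form is a difference in mean change of 4 × .10 = 0.4 SD. Power is .999 before adjustment and above .999 after it (r = .5). There is no material gain.

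**4. Power at 0.20 SD.** With v the variance from step 2, SE = √[v(1/375 + 1/375)] against pooled controls and √[v(1/375 + 1/187.5)] against the active control alone. Power ≈ Φ(0.20/SE - 1.96).

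For example, against pooled controls at r = .5: the change-score SE is √(2/375) = .0730, so power is Φ(2.74 - 1.96) = .78. The adjusted SE is √(.75 × 2/375) = .0632, so power is Φ(3.16 - 1.96) = .89.

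| r | pooled controls: change → adjusted | active control alone: change → adjusted |
|---|---|---|
| .3 | .64 → .82 | .47 → .65 |
| .5 | .78 → .89 | .61 → .73 |
| .7 | .94 → .97 | .82 → .88 |
| .9 | above .99 both | above .99 both |

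**5. More than one follow-up.** If the mean of two follow-ups is analysed under compound symmetry, the cut is 33%, 27% and 20% at r = .5, .6 and .7. The figures in step 2 apply to a single follow-up only.

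**The case against.** The strongest reply is that the plan loses nothing it was counting on. At its stated inputs power is .999 either way. The gains above come from choosing 0.20 SD. At 0.27, which section 1.1 cites for technology-assisted interventions, the pooled contrast goes from .96 to .99 at r = .5 and is above .99 both ways at r = .7; the active-control contrast goes from .86 to .94 and from .97 to .99. That stands: the benefit is modest unless effects are small, and section 1.1 itself reports a critique that true effects are probably smaller than published.

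Three further points also stand.
- The identity with change scores is exact only for two time points. The data-analysis wording does not limit the ANOVA to two, although the power analysis refers to one follow-up.
- The additional mixed model leaves room for M1. It is under-specified on this point, not shown to be inefficient. It would share the loss only if M1 were modelled as an outcome with a free mean in each arm.
- A reader might infer that change scores are biased by chance baseline imbalance, as a second fault beside the lost precision. They are not. The variance difference is 2(1-r) - (1-r²) = (1-r)², which is the contribution of baseline imbalance itself, so it is one loss and not two. Under randomisation the change-score estimate is unbiased.

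A reader might also take 15 to 25% as the established saving. That range is only the result for r between .5 and .7, and the documents support no particular r. The r of .5 that reproduces .999 is a reconstruction, not a stated assumption.

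**Conclusion.** The point holds as a matter of efficiency. With M1 and one follow-up, the planned interaction test is a valid comparison of raw change, and adjusting for M1 is more precise for every r below 1. The saving is (1-r)/2 of the variance: 35% to 5% over an assumed r of .3 to .9. At the plan's own effect size it does not alter the power. It narrows confidence intervals and helps power for smaller effects, most visibly at low r and for the active-control contrast.

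The figures rest on equal SDs, complete M1, a single follow-up, 50% attrition spread evenly over the arms, and a 0.20 SD effect that is not the plan's planning value. The documents do not support calling the planned test wrong or the trial underpowered on this ground. The change is worth making because it is specific and nearly free.

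**What to change.** Replace the two-way mixed ANOVA, as the effect analysis, by an ANCOVA: the 10-week score (intervention M3, control M2) on arm, with the M1 score of the same scale as covariate. State the assumed r with any power quoted for this test.

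An alternative is a constrained longitudinal model with one M1 mean common to all arms and arm effects at follow-up only. Two conditions apply.
- It must be restricted to the shared times before crossover: baseline, 10 weeks and 5 months. Outside these the visits do not line up between arms. No participant has both the intervention arm's one-month visit and the controls' own booster visit, so an unstructured covariance over all visits could not be estimated, and later control visits follow treatment.
- M1 must be answered before allocation is known. The text places M1 at registration and also just before the main webinar, and the timeline figure was not available to this review, so the plan should say so explicitly.

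This model is related to the ANCOVA but not identical, because it also uses participants with incomplete follow-up; with 50% attrition expected, the two can differ.

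The cost is a few sentences of analysis text, fixed at preregistration, and one degree of freedom for the covariate. No new data or participants are needed.

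### The 12-month effects in research question 2 have no concurrent untreated randomised comparator, and the five-time-point model names no time scale, exposure term or between-group contrast

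*Combined protocol and SAP*

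**What the plan says.** All of this is in section 1.3 unless stated.

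- **Research questions.** Question 2 reads "To what extent are the effects short-term and long-term (i.e., 10 weeks and 12 months", and so applies one word, effects, to both horizons.
- **Sample and Design.** 750 participants go to the intervention and 375 to each of two wait-list groups. Both wait-list groups receive the intervention five months later.
- **Procedures, intervention group.** After baseline, visits are "at the booster session webinar one months after the completed main webinar (M2), 10 weeks after the main webinar (M3"), then "five months after the main webinar (when control groups are starting) (M4) and 12 months after the intervention is completed (M5").
- **Procedures, control groups.** After baseline, visits are "when the interventions group has completed the intervention (M2), when they start the intervention (main webinar) (M3"), then the controls' own booster session (M4), then "ten weeks after the main webinar (M5) and 12 months after the intervention is completed (M6").
- **Data analysis.** The effect analysis is a two-way mixed ANOVA on wellbeing at measurement points that are not named. The plan continues: "In addition, we will run a longitudinal analysis using linear mixed (multilevel) models on the data from all five measurement time points". It adds that "Mixed modelling is a flexible way to handle unbalanced data", and that hypotheses are tested "while controlling for both stable and time-varying covariates".
- **Power analysis.** The stated power of .999 is for 750 participants at the second measurement point.
- **Section 3.2, work plan.** A between-group comparison is listed separately from 12-month rows for the intervention group and for the control groups.

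Figure 2, which shows the visit schedule, is not available in the text reviewed, so the schedule here comes from the Procedures wording alone.

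**The concern.** Two things are at issue.

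First, a randomised effect needs a comparator that has not been treated at that time. By month 12 every control has been offered the intervention. A 12-month change in the intervention group is then open to regression to the mean, season, recovery from the pandemic and selective dropout. The plan as worded lets such a change be reported as an effect. That matters because section 2.1 justifies the trial by the need to establish causality.

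Second, the same visit number means a different week in each arm, and two or more of the control visits follow the controls' own webinar. A group-by-time interaction over all five numbered visits is a treatment effect only if time and exposure are coded suitably. The analysis text does not say how they will be.

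**Working it through.** **1. The plan's own figure.** Noncentral F for the interaction: λ = N·m·f²/(1−ρ), with N = 750, m = 2, f = 0.10, and ρ = 0.5 assumed because none is stated. λ = 750 × 2 × 0.01 / 0.5 = 30. Power at α = .05 is .9992 with three groups (df 2, 747) and .9998 with two (df 1, 748). The stated .999 reproduces. It covers two measurement points, so it supports neither a 12-month question nor a five-point model.

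**2. Visits in weeks from the intervention group's main webinar.** One month = 365.25/12/7 = 4.35 weeks; M1 is taken as week 0 in both arms; gaps use unrounded weeks.

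| Visit | Intervention | Control | Gap |
|---|---|---|---|
| M1 | 0 | 0 | 0 |
| M2 | 4.3 | 10 | −5.7 |
| M3 | 10 | 21.7 (own webinar) | −11.7 |
| M4 | 21.7 | 26.1 (treated) | −4.3 |
| M5 | 10 + 52.2 = 62.2 | 31.7 (treated) | +30.4 |
| M6 | none | 83.9 (treated) | n/a |

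No post-baseline pair with the same number falls in the same week. Two untreated same-week pairs do exist: intervention M3 with control M2 (week 10), and intervention M4 with control M3 (week 21.7). At week 62 the controls were treated 62.2 − 21.7 ≈ 40 weeks earlier and have no visit. Counting 12 months from the webinar (about week 52) changes nothing, as the nearest control visits are still weeks 32 and 84.

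**3. A real effect, visits matched by number, no treatment term.** Take a constant, lasting effect of 0.20 SD, present from the first visit after each arm's webinar. Intervention minus control at M2 to M5 is 0.20, 0.20, 0, 0, averaging 0.10. Each same-week pair would show 0.20.

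**4. No effect, shared linear drift, same matching.** Expected difference at each visit: d = drift × gap / 52.18. With equal groups of n, controls pooled and compound symmetry, λ = (n/2)·Σ(d − mean d)²/(1−r), df₁ = T−1, df₂ = (2n−2)(T−1). For five visits the squared gap deviations sum to 1,100. At 0.10 SD per year, Σ = 1,100 × (0.10/52.18)² = 0.00404. For n = 375, r = .5: λ = 187.5 × 0.00404 / 0.5 = 1.52, rejection rate .138.

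| Drift, SD/year | n | r = .5 | r = .7 |
|---|---|---|---|
| 0.05 | 188 | .060 | .066 |
| 0.05 | 375 | .070 | .084 |
| 0.10 | 188 | .091 | .122 |
| 0.10 | 375 | .138 | .209 |

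Over M1 to M3 only, the rates are .051 to .062 across the same settings. The inflation comes mostly from M5, where week 62 is set against week 32.

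**5. Uncontrolled change at week 62, no effect.** This does not depend on coding. Change = drift × 62.2/52.18, which is 0.060 or 0.119 SD. SE = √(2(1−r)/n), which runs from 0.073 (n = 188, r = .5) to 0.040 (n = 375, r = .7). By normal approximation the change is significant in 13-32% of trials at 0.05 SD per year and 37-85% at 0.10.

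Here n = 375 is half of the 750 expected at the second measurement point, and 188 is half of that again. The documents give no number followed at M5, no r and no drift.

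**The case against.** The strongest reply is that the plan is unspecified rather than wrong. Mixed models accommodate unbalanced visits, and the text allows time-varying covariates, so a correct exposure term is possible. The five-point model is supplementary to the ANOVA. The work plan separates the between-group comparison from the per-group 12-month rows, and no sentence plans a causal between-group claim at 12 months. Figure 2 might settle the labelling. All of this stands, and it limits the point. None of it supplies a time scale, an exposure term or named contrasts, and research question 2 still speaks of effects at 12 months.

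Four stronger readings are tempting and not supported:

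- *The plan will put treated controls, uncoded, into the between-group contrast.* Including them is the natural reading of five time points, but how they will be coded is not stated.
- *A 12-month result can only be within-group change.* Start time is randomised and staggered, so a model with calendar time and exposure time could estimate a longer-term effect, under assumptions that include extrapolating the time trend.
- *The two statements of five months conflict, so the five-month pair may not align.* The Design wording is loose, but Procedures ties intervention M4 to the start of the control groups.
- *The trial's false-positive rate is badly inflated.* That needs matching by visit number, no treatment term and appreciable drift. At 0.05 SD per year the five-point rate is 6-8%, and over M1 to M3 it stays close to 5%. Comparing treated with treated at M4 and M5 dilutes a lasting benefit; it does not create one.

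**Conclusion.** The point holds and should be fixed. It is certain from the text that no concurrent untreated randomised comparison exists at 12 months, and that the stated five time points do not match the controls' six visits. It is also clear that the Procedures text contains two valid same-week contrasts to which the analysis text does not commit.

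The numerical size is illustrative. Matched by number with no treatment term, a lasting 0.20 SD effect is halved on average over M2 to M5, and the five-point interaction is falsely significant in about 6-8% (drift 0.05) or 9-21% (drift 0.10) of trials. The larger exposure is uncontrolled change at week 62, at 13-32% or 37-85%. These figures assume shared linear drift, compound symmetry, r of .5 to .7, 188 to 375 per group and pooled controls. The missing 12-month comparator depends on none of these assumptions.

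**What to change.** 1. In research question 2, name 10 weeks and five months as the randomised effects. Label 12-month results as maintenance without a concurrent untreated control.
2. Code time as weeks since baseline. Take the between-group effect from intervention M3 against control M2 (week 10) and intervention M4 against control M3 (five months), and state that control M3 is completed before the controls' webinar.
3. Leave control data after their own webinar out of the between-group model, or code them with a time-varying exposure term.
4. Correct the number of time points to five for the intervention group and six for the control groups.

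The cost is wording and model coding, with no new participants, visits or data. The downside is that no randomised 12-month claim can be made, which the design never supported.
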